7.4.2 Modifications of Study Therapy

7.4.2.1 Dose Delays

For nivolumab, treatment may be delayed for up to a maximum of 6 weeks from the last dose. Subjects receiving nivolumab may be dosed no less than 12 days from the previous dose.

Each study medication infusion may be delayed independently. A dose will be considered as actually delayed if the delay is exceeding 3 days (i.e., greater than or equal to 4 days from scheduled dosing date) from previous dose for any given study medication. The length of delay for nivolumab is defined as (duration of previous cycle in days - 14). The length of delay for ipilimumab is defined as (duration of previous cycle in days - 42). Dose delays for each study medication will be divided into following categories: on-time, 4 - 7 days, 8 - 14 days, 15 - 42, > 42 days. Reason for dose delay will be retrieved from the respective CRF dosing pages for each study medication. If different reasons for delay are recorded (in the same cycle), both the reasons will be reported.

The following parameters will be summarized by cohort and treatment group.

- Number of subjects with at least one dose delayed, number of dose delayed per subject, Length of Delay and Reason for Dose Delay

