Tumor Assessment	X (See note)		Contrast enhanced MRI after 6 & 12 weeks (± 1 week) then Q 8 weeks (± 1 week) X 4, then Q 12 weeks , (± 1 week) or earlier if clinically indicated. Post-RT MRI required in Cohort 1. MRI of the spine also performed per clinical indication. See Section 9.1.1 .
Dispense Study Drug	X (combination)	X (monotherapy)	First dose within 3 calendar days of treatment assignment.

- ^a If a dose is delayed, the procedures for that same time point should also be delayed to coincide with when that time point's dosing actually occurs, except tumor assessments which should follow the specified schedule. Cycle 5 begins 3 weeks after Cycle 4
- ^b Some of the assessments referred to in this section may not be captured as data in the eCRF. They are intended to be used as safety monitoring by the treating physician. Additional testing or assessments may be performed as clinically necessary or where required by institutional or local regulations.

Figure 2.-2: Module B Treatment and Key Assessments

Module B: Treatment & Key Assessments

This Figure is for overall guidance, and does not include (eg) treatment delay, unscheduled assessments, etc.

- | Nivolumab | Ipilimumab
- X Tumor sample; and if surgery on-study or at PD
- ▲ ▼ PK: pre-dose & EOI; ADA samples
- ▲ Biomarker samples; see Table for detail
- ▲ MRI scan: pre-study, q6 wk x 2, then q8 wk
- □ Local lab tests, repeat as clinically indicated

Table 2.-4: Follow-up Procedural Outline (CA209908)

Procedure	Follow-up Visits 1 & 2 ^a	Survival Visits ^b	Notes ^c
Targeted Physical Examination	X		
Adverse Events Assessment	X	X	Drug-related adverse events will be followed until resolved or returned to baseline. See Section 9.2.3 .
Serious Adverse Events Assessment	X		
Laboratory Tests	X		CBC w/differential, LFTs, T. Bili, BUN, creatinine, Na, K, Cl, glucose and TSH for follow-up #1, repeat labs at follow-up #2 if study drug-related toxicity persists.
Pregnancy Test WOCBP only	X		Serum or Urine.
████████████████████	█		
████████████████████	█		████████████████████ ████████████████████
Survival Status	X	X	Every 3 months (clinic visit or telephone contact), during Survival phase, include documentation of subsequent chemotherapy.

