7.4.1 Administration of Study Therapy

The following parameters will be summarized (descriptive statistics) by cohort, study therapy (nivolumab and ipilimumab) and treatment group:

- Number of doses received
- Cumulative dose
- Relative dose intensity (%) using the following categories: < 50%; 50 - < 70%; 70 - < 90%; 90 - < 110%; ≥ 110%.

Duration of treatment will be presented by treatment group using a Kaplan-Meier curve whereby the last dose date will be the event date for those subjects who are off study therapy. Median duration of treatment and associated 95% CI will be provided. Subjects who are still on study therapy will be censored on their last dose date.

A by-subject listing of dosing of study medication (record of study medication, infusion details, and dose changes) and a listing of batch numbers will be also provided.

The key parameters used to calculate dosing data are shown below.

Table 7.4.1-1: Study Therapy Parameter Definitions

Monotherapy of Nivolumab		
Nivolumab		
Dosing schedule per protocol	3 mg/kg every 2 weeks	
Dose	Dose (mg/kg) is defined as Total Dose administered (mg)/Most recent weight (kg). Dose administered in mg at each dosing date and weight are collected on the CRF.	
Cumulative Dose	Cum dose (mg/kg) is sum of the doses (mg/kg) administered to a subject.	
Relative dose intensity (%)	Cum dose (mg/kg)/[(Last dose date - Start dose date + 14) x 3/14] x 100	
Duration of treatment	Last dose date - Start dose date +1	
Nivolumab combined with Ipilimumab		
	Nivolumab	Ipilimumab
Dosing Schedule per Protocol	3 mg/kg every 3 weeks for 4 doses followed by 3 mg/kg every 2 weeks	1 mg/kg every 3 weeks for 4 doses
Dose	Dose (mg/kg) is defined as Total Dose administered (mg)/Most recent weight (kg). Dose administered in mg at each dosing date and weight are collected on the CRF	Dose (mg/kg) is defined as Total Dose administered (mg)/Most recent weight (kg). Dose administered in mg at each dosing date and weight are collected on the CRF
Cumulative Dose	Cum Dose (mg/kg) is the sum of the doses administered to a subject.	Cum Dose (mg/kg) is the sum of the doses administered to a subject.
Cycle Duration _(i) (wk)	(Dose date _(i+1) - Dose date _(i))/7	N/A
Cycle Intensity _(i) (mg/kg/wk)	Dose _(i) /Cycle Duration _(i)	N/A
Relative Cycle Intensity _(i) (%)	(Cycle Intensity _(i) /intended dose per week) * 100	N/A

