Relative Dose Intensity (%)	Sum of all Relative Cycle Intensities divided by N	Cum dose /[(Last dose date - Start dose date + 21) x 1/21] x 100
Duration of Treatment	Last dose date - Start dose date +1	Last dose date - Start dose date +1

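### SAP 7.4.2.1 measures Module B dose delays from the wrong intervals (7 days too long for nivolumab doses 2-5, 21 days too short for ipilimumab); separately, the temozolomide deviation check in SAP 7.2.2 does not fit Cohort 1 eligibility

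*SAP*

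**What the plan says.** **Delay length.** SAP 7.4.2.1 gives one formula per drug, with no split by module or cycle:

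- Nivolumab: "The length of delay for nivolumab is defined as (duration of previous cycle in days - 14" (bracket closes after the number).
- Ipilimumab: "The length of delay for ipilimumab is defined as (duration of previous cycle in days - 42" (likewise).

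The same section calls a dose delayed when it is "greater than or equal to 4 days from scheduled dosing date". It sorts delays into on-time, 4-7, 8-14, 15-42 and over 42 days, and lists length of delay among the parameters to be summarised by cohort and treatment group.

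**Schedule.** SAP Table 7.4.1-1 gives nivolumab in combination as "3 mg/kg every 3 weeks for 4 doses followed by 3 mg/kg every 2 weeks", and ipilimumab on the same 3-weekly schedule for four doses. Protocol Table 2.-3, footnote a, adds "Cycle 5 begins 3 weeks after Cycle 4"; Protocol 7.1.2 agrees. The SAP's ipilimumab relative dose intensity is "Cum dose /[(Last dose date - Start dose date + 21) x 1/21] x 100", which also uses 21 days.

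**Neighbouring statements.** SAP 7.4.2.1 says "For nivolumab, treatment may be delayed for up to a maximum of 6 weeks from the last dose" and "Each study medication infusion may be delayed independently". Protocol 8.1.1 sets a 6-week limit for monotherapy, Protocol 8.1.2 sets 8 weeks during combination therapy, and Protocol 7.4.1 has the two Module B drugs held together.

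**Deviation check.** SAP 7.2.2 lists as a programmable entry deviation, for Cohorts 1a and 1b only, the lack of first-line radiotherapy plus temozolomide. Protocol 6.1, criterion 2.a.i, admits to Cohort 1 participants with DIPG who have had radiotherapy and no chemotherapy.

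**The concern.** A dose given exactly on schedule should have a delay length of zero. That requires the subtracted constant to equal the scheduled interval. For the Module B combination doses the interval is 21 days, and neither 14 nor 42 equals it. No place in either document schedules ipilimumab every 6 weeks; in SAP 7.4.2.1 the only other 6-week figure is the maximum nivolumab delay, which is not a dosing interval.

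Safety and tolerability of the combination is an objective of the study, and dose delay is one of the ordinary measures of it. Followed as written, the Module B summary overstates nivolumab delays and understates ipilimumab delays, although the protocol has the two drugs held together. A programmer who quietly corrected the constants would produce output that departs from the SAP.

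The deviation check has a similar fault: it tests for a treatment history that the Cohort 1 criterion excludes.

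**Working it through.** **Inputs.** Constants 14 and 42, the delay categories and the 6-week limit: SAP 7.4.2.1. Module B interval 21 days for ipilimumab doses 2-4 and nivolumab doses 2-5, then 14 days for nivolumab: SAP Table 7.4.1-1, Protocol Table 2.-3 and 7.1.2. Dosing window of 3 days either side: Protocol 7.1. Combination limit of 8 weeks: Protocol 8.1.2. Planned treated in Module B, 80: Protocol Synopsis.

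**Check of the constants on a perfectly timed series**

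- Module A nivolumab: 14 − 14 = 0. Correct.
- Module B nivolumab, days 0, 21, 42, 63, 84, 98, 112: doses 2-5 give 21 − 14 = +7; dose 6 onward gives 14 − 14 = 0.
- Module B ipilimumab, days 0, 21, 42, 63: doses 2-4 give 21 − 42 = −21.
- The SAP's dose-intensity formula with 21 gives four on-time ipilimumab doses 4 / [(63 + 21)/21] × 100 = 100%. With 42 it would give 4 / [(63 + 42)/42] × 100 = 160%. So 42 is not the interval the SAP uses elsewhere.

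**General result.** For a dose d days late, nivolumab doses 2-5 give (21 + d) − 14 = d + 7, and ipilimumab doses 2-4 give (21 + d) − 42 = d − 21. The gap is 28 days.

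| True delay d | True category | Nivolumab length → category | Ipilimumab length → category |
|---|---|---|---|
| −3 to 0 | on-time | 4 to 7 | −24 to −21 |
| 1 to 3 | on-time | 8 to 10 | −20 to −18 |
| 4 to 7 | 4-7 | 11 to 14 → 8-14 | −17 to −14 → below 4 |
| 8 to 14 | 8-14 | 15 to 21 → 15-42 | −13 to −7 → below 4 |
| 15 to 24 | 15-42 | 22 to 31 → 15-42 | −6 to 3 → below 4 |
| 25 to 28 | 15-42 | 32 to 35 → 15-42 | 4 to 7 → 4-7 |
| 29 to 35 | 15-42 | 36 to 42 → 15-42 | 8 to 14 → 8-14 |
| 36 to 42 | 15-42 | 43 to 49 → over 42 | 15 to 21 → 15-42 |
| 43 to 63 | over 42 | 50 to 70 → over 42 | 22 to 42 → 15-42 |
| 64 or more | over 42 | 71 or more → over 42 | 43 or more → over 42 |

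The rows beyond d = 35 arise only under the exceptions in Protocol 8.1.2.

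**Two readings of the flag.** If the computed length decides both the flag and the on-time class (taken as under 4 days), on-time nivolumab doses 2-5 count as delayed, and ipilimumab delays of 4-24 days count as on-time. If the scheduled date decides the flag, counts of delayed doses are right. Ipilimumab delays of 4-24 days then carry lengths of −17 to +3, which fit no delay category. The lengths are wrong under both readings.

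**Share of day values of d in the wrong category**, assuming a delay limit applies to both drugs and to the dose 4-5 interval:

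- 42-day maximum interval, d = 4 to 21 (18 values): ipilimumab 18 of 18; nivolumab 11 of 18 (d = 4 to 14).
- 56-day maximum interval, d = 4 to 35 (32 values): ipilimumab 32 of 32 (21 below 4 days, 11 too low); nivolumab 11 of 32.

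**Intervals exposed, at most.** Nivolumab 80 × 4 = 320; ipilimumab 80 × 3 = 240.

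**Deviation check.** If 1a and 1b mean A1 and B1, every compliant participant is flagged, up to 2 × 22 = 44, and one who had radiotherapy plus temozolomide is not. If the labels match no cohort, the check flags nobody.

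**The case against.** The strongest reply is that the delayed/not-delayed flag is tied to the scheduled dosing date, so a programmer could get the counts right, and the more alarming misclassifications need the weaker reading. That is fair as far as the flag goes. It does not rescue length of delay, which is a summary of its own.

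The counts of day values are not expected numbers of doses. The 320 intervals assume that all 80 participants reach dose 5 on day 84 (84/30.4375 = 2.76 months), while the historical median PFS figures for Cohorts 2 and 4 are 2.25 and 2.1 months. Both points stand: 320 and 240 are ceilings.

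The labels 1a and 1b appear nowhere else in the available text, and the line may be carried over from another plan; SAP section 10 shows that version 2.0 removed another item as not relevant to this study. The figure of 44 is therefore conditional. What is certain is that the line is either inverted or empty.

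The sentence on independent delay may only mean that delays are derived per drug, so its conflict with Protocol 7.4.1 is the weakest part.

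There are safeguards. The dosing listings (SAP 7.4.1) and prior-agent summary (7.3.4) keep the underlying data, delay-related adverse events follow the Core Safety SAP (7.6.4), DLT evaluability has its own delay rule (4.1.1), and other deviation listings exist (7.2.2). The standard-of-care check in 7.2.2 may help less: it looks for missing therapy, so it would not obviously catch added chemotherapy. None of these corrects the summary tables.

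**Conclusion.** The concern holds. As written, length of delay in Module B is 7 days too long for nivolumab doses 2-5 and 21 days too short for ipilimumab doses 2-4, under either reading of the flag. Module A, and Module B nivolumab from dose 6 on, are unaffected. The category errors rest on the stated delay limits applying to both drugs; the length errors need only the schedule on which the protocol and SAP agree. The Cohort 1 temozolomide check cannot serve its purpose under either interpretation of its labels.

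The consequences are confined to descriptive exposure and deviation tables. No primary test, power figure or stopping rule changes. The correction should be made, but it does not threaten the study's conclusions on efficacy.

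**What to change.** **SAP 7.4.2.1.**

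- Define length of delay as the actual interval minus the interval the protocol schedules for that dose: in Module B, 21 days for ipilimumab and for nivolumab doses 2-5, then 14 days; in Module A, 14 days.
- Use this single length for both the 4-day flag and the categories, and define on-time as a length below 4 days. Doses earlier than the protocol window can be listed separately, so that they do not pass as on-time.
- State which scheduled interval the derivation takes from the protocol when nivolumab continues alone after early ipilimumab discontinuation; the available text does not give it.
- Reconcile the 6-week statement with the separate monotherapy and combination limits in Protocol 8.1.1 and 8.1.2, and the sentence on independent delay with Protocol 7.4.1.

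**SAP 7.2.2.** Replace the temozolomide line with a check for Cohorts A1 and B1 that follows the protocol criterion: no radiotherapy, or any chemotherapy, before the first dose of study treatment. First dose is the right reference date because Protocol 5.1.1 lets Cohort 1 enrol before radiotherapy is complete.

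**Cost.** SAP wording and derivation code. No new data are needed, and the derivations need no protocol change.

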7.4.2.2 Infusion Interruptions and Rate Changes

[figure not shown]
Each nivolumab or ipilimumab infusion can be interrupted and/or the IV infusion rate can be reduced. This information will be retrieved from CRF dosing pages

The following parameters will be summarized by cohort and treatment group:

- Number of subjects with at least one dose infusion interruption, number of infusion interruptions per subject and the reason for interruption.
- Number of subjects with at least one IV infusion rate reduction, number of IV infusion rate reduction per subject and the reason for reduction

7.4.2.3 Dose Reductions/Escalation

There will be no dose escalations or reductions of nivolumab allowed.

7.5 Efficacy

The primary efficacy analyses will be performed on treated population for the final analysis. Unless otherwise specified, all analysis will be performed separately for each cohort and treatment group.

7.5.1 Overall Survival

7.5.1.1 Overall Survival for Cohort 1

As the primary efficacy endpoint of Cohort 1, the OS is defined as the time between the date of diagnosis and the date of death. A participant who has not died will be censored at the last known alive date.

The OS curves for each treatment group will be estimated using the Kaplan-Meier (KM) product-limit method. Median OS and the corresponding two-sided 80% confidence intervals using the log-log transformation will be computed.

The distribution of OS will also be compared against the historical control of an exponential distribution with median OS 9 months [REDACTED] using a one-sided one-sample log rank test when approximately 17 events have occurred or after each participant has been followed for at least 24 months.

As one of the secondary endpoints, survival rate at 12 months will be estimated using KM estimates on the OS curve and its corresponding 95% confidence interval will be derived based on Greenwood formula.

7.5.1.2 Overall Survival for Cohorts 2 to 4

As the secondary efficacy endpoints of cohorts 2 to 4, the OS is defined as the time between the first dose date and the date of death. A participant who has not died will be censored at the last known alive date.

The OS curves for each treatment group will be estimated using the Kaplan-Meier (KM) product-limit method. Median OS and the corresponding two-sided 95% confidence intervals using the log-log transformation will be computed.

Survival rate at 12 month will be estimated using KM estimates on the OS curve and its corresponding 95% confidence interval will be derived based on Greenwood formula.

7.5.1.3 Overall Survival for Cohort 5

OS will be listed. OS curve will be computed using Kaplan-Meier method for pooled indications and selected individual indications. The corresponding 95% confidence interval for median OS will be calculated via Brookmeyer and Crowley methodology using log-log transformation.

7.5.1.4 Subjects Follow Up

The extent of follow-up defined as the time between the first dose date (diagnosis date for cohort 1) and last known date alive (for subjects who are alive) or death date (for subjects who died). It will be summarized descriptively (median, min, max) for all treated subjects.

The currentness of follow-up, defined as the time between last OS contact (i.e., last known date alive or death date) and data cut-off date, will be summarized by treatment group. Subjects who died and subjects with a Last Known Date Alive on or after LPLV will have a value of '0' for currentness of follow-up. The currentness of follow-up will be categorized into the following categories: 0 days, 1-30 days, 31-60 days, 61-90 days, 91-120 days, 120-150 days, 151 or more days.

7.5.2 Progression Free Survival

For all cohorts, progression free survival (PFS) is defined as the time from first dose to the date of the first documented tumor progression or death due to any cause. Participants who die without a reported prior progression will be considered to have progressed on the date of death. Participants who did not have disease progression or die will be censored at the date of last evaluable tumor assessment. Participants who did not have any on study tumor assessment and did not die will be censored at the first dose date. PFS will be determined by investigators based on RANO criteria. First tumor assessments will occur at week 6 and 12, and will be at every 8 weeks for the first year and then every 12 weeks thereafter until disease progression is documented

7.5.2.1 Progression Free Survival for Cohorts 1

As one of the secondary endpoints of Cohort 1, PFS is estimated by Kaplan-Meier method and the corresponding 95% CI for median PFS will be calculated via Brookmeyer and Crowley methodology using log-log transformation. It will be analyzed at the time of the primary analysis.

7.5.2.2 Progression Free Survival for Cohorts 2 to 4

As the primary efficacy endpoints of cohorts 2 to 4, PFS curve will be estimated using the Kaplan-Meier (KM) method. Median PFS and the corresponding two-sided 80% confidence intervals using the log-log transformation will be computed.

The distribution of PFS for cohort 2 will be compared against the historical control of an exponential distribution with median PFS 2.25 months [REDACTED] using a one-sided one-sample log rank test when each participant has been followed for at least 12 months.

The distribution of PFS for cohort 3 will be compared against the historical control of an exponential distribution with PFS(4) equal to .18 using a one-sided one-sample log rank test when either 15 events have occurred or each participant has been followed for at least 12 months.

The distribution of PFS for cohort 4 will be compared against the historical control of an exponential distribution with median PFS equal to 2.1 months using a one-sided one-sample log rank test when either 10 events have occurred or each participant has been followed for at least 12 months.

In addition, as one of the secondary endpoints, PFS rate at 6 months will be estimated using KM estimates on the PFS curve and its corresponding 95% confidence interval will be derived based on Greenwood formula.

7.5.2.3 Progression Free Survival for Cohort 5

For each treatment group separately individual PFS will be listed by tumor type after each participant reaches 12 months follow-up. PFS curve will be estimated using the Kaplan-Meier (KM) method for all tumor types (pooled) and selected individual tumor types, if there is enough data. [REDACTED]

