9.1.1 Imaging Assessment for the Study

All participants will undergo contrast enhanced brain MRI at the time points specified in [Table 2-1](#), [Table 2-2](#), [Table 2-3](#), and [Table 2-4](#). An Imaging Manual will be provided. Screening MRI may be performed prior to informed consent, as part of standard care. Adequate quality of the baseline evaluation must be assured by the PI prior to treatment start and repeat imaging performed if not adequate. However, it is not necessary that the MRI machine be “qualified” (by imaging CRO) for the screening evaluation.

For Inclusion of Cohorts 2-5, if first recurrence of the CNS tumor is documented by MRI, an interval of at least 12 weeks after the end of prior radiation therapy is required unless there is either: i) histopathologic confirmation of recurrent tumor, or ii) new enhancing mass on MRI outside of the radiotherapy treatment field.

Evaluation of the leptomeninges is standard in many pediatric CNS malignancies and should be performed as clinically indicated. In Cohorts 3 and 5, a baseline MRI spine and CSF cytopathology are expected, unless clinically contraindicated. In Cohorts 2 and 4, baseline MRI spine and CSF cytopathology may be obtained based on clinical judgment; these are not expected in Cohort 1.

On treatment and follow up MRIs should occur on the following schedule: Q6W x 2 assessments, then Q8W x 4, and then Q12W (\pm 1 week). The expected timing of tumor assessments is therefore at Weeks 7, 13, 21, 29, 37, 45, and subsequently every 12 weeks. Investigators may obtain more frequent follow-up MRI scans as medically indicated. Local radiologic assessment of tumor measurements will be used during the study for clinical management and investigator-assessed disease progression. MRI scans should continue on the indicated schedule regardless of treatment delay.

If baseline MRI spine showed metastatic deposits, then it should be repeated at the same intervals as the MRI of brain, ie regular tumor assessments indicated in [Table 2-2](#), [Table 2-3](#), and [Table 2-4](#), ordinarily at the same imaging session. Frequency of MRI spine is at the investigator’s discretion. If the baseline is negative, then less frequent re-assessment may be appropriate depending on the individual circumstances. All imaging assessments of sites of disease should be submitted ([Section 5.1.6.3](#)) to the central imaging laboratory.

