4.1.2 Expansion Phase

4.1.2.1 Overall Survival for Cohort 1

The primary endpoint of Cohort 1 is overall survival (OS). OS for Cohort 1 is defined as the time between the date of diagnosis and the date of death in Cohort 1. A participant who has not died will be censored at the last known alive date. OS will be followed continuously while participants are on study drug and every 3 months via in-person or phone contact during the survival follow-up phase of the study drug.

4.1.2.2 Progression Free Survival for Cohorts 2 to 5

The primary endpoints of Cohort 2-5 are progression-free survival (PFS).

PFS is defined as the time from first dose to the date of the first documented tumor progression or death due to any cause. Participants who die without a reported prior progression will be considered to have progressed on the date of death. Participants who did not have disease progression or die will be censored at the date of last evaluable tumor assessment. Participants who did not have any on study tumor assessment and did not die will be censored at the first dose date. PFS will be determined by investigators based on RANO criteria. First tumor assessments will occur at week 6 and 12, and will be at every 8 weeks for the first year and then every 12 weeks thereafter until disease progression is documented.

Table 4.1.2.2-1: Censoring Scheme used in Analysis of PFS

Situation	Date of Progression or Censoring	Outcome
No baseline tumor assessments	First dose date	Censored
No on study tumor assessments and no death	First dose date	Censored
Documented progression	Date of the first documented progression per RANO	Progressed
Diagnostic surgical resection without documented progression prior or on the same day and without confirmed disease progression from tumor pathology	Date of last tumor assessment prior to initiation of the diagnostic surgical resection	Censored
No progression and no death	Date of last assessment for disease progression	Censored
Subsequent therapies, including new anticancer therapy, tumor-directed radiotherapy, or tumor-directed surgery received, without progression reported prior or on the same day	Date of last assessment for disease progression prior to initiation of the subsequent therapy	Censored
Death without progression	Date of death	Progressed

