5 SAMPLE SIZE AND POWER

By applying the above methodology, the intended target number of participants (N) for cohort 1-4 are obtained as follows:

Cohort 1: 22 participants are required (17 events) for each cohort. This assumes 80% power with a one sided Type 1 error of 10%, a historical median OS of 9 months [REDACTED], 1-year accrual, 2-year follow-up, and a target effect size of median OS 15 months.

Cohort 2: 15 participants are required for each cohort. This assumes 80% power with a one-sided Type 1 error of 10%, a historical PFS(6) of 18% [REDACTED], one-year accrual, one-year follow-up, a target PFS(6) of 38%. An interim analysis based on PFS(6) for futility only will be conducted after at least 8 of the planned number of participants are enrolled with 6 months follow-up. In addition, all other available efficacy data will be evaluated in the futility analysis. [REDACTED]

[REDACTED] Details of the futility criteria and simulations will be contained in the Statistical Analysis Plan (SAP).

Cohort 3: 15 participants are required for each cohort. This assumes 80% power with a one-sided Type 1 error of 10%, 1-year accrual and 1-year follow-up, a historical median PFS(4) of 18% and a target PFS(4) of 38% ([REDACTED] equivalent to PFS(6) of 23%). An interim analysis based on PFS(6) for futility only will be conducted after at least 8 of the planned number of participants are enrolled with 6 months follow-up. In addition all other available efficacy data will be evaluated in the futility analysis.

Cohort 4: 10 participants are required for each cohort. This assumes at least 80% power with a one-sided Type 1 error of 10%, a historical median PFS of 2.1 months [REDACTED], 1-year accrual, 1-year follow-up, and a target median PFS of 4.4 months.

Cohort 5: 18 participants are required for each cohort. Sample sizes each of the expansion Cohorts A5 and B5 is not based on statistical considerations as these cohorts contain various tumor types. However, if the disease control rate at 12 months is 30%, 18 participants provide 21% precision for the estimate.

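### The stated 10% one-sided error of the primary PFS tests in Cohorts 2–4 is not assured, because progression is dated at the detecting scan while expected events come from a continuous exponential null

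*SAP*

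**What the plan says.** SAP 7.5.2 measures PFS from first dose to first documented progression or death. The censoring table in SAP 4.1.2.2 dates a progression at "Date of the first documented progression per RANO". Protocol 9.1.2 moves a confirmed progression back to the assessment that first showed it, but no earlier.

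The scan grid is in Protocol 9.1.1: "The expected timing of tumor assessments is therefore at Weeks 7, 13, 21, 29, 37, 45, and subsequently every 12 weeks". That means scans after 6, 12, 20, 28, 36 and 44 completed weeks.

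SAP 7.5.2.2 sets these times against a continuous curve by a one-sided one-sample log-rank test. Cohort 2 uses a "historical control of an exponential distribution with median PFS 2.25 months"; for Cohort 3, "The distribution of PFS for cohort 3 will be compared against the historical control of an exponential distribution with PFS(4) equal to .18"; Cohort 4 uses a median of 2.1 months.

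SAP 5 gives the operating characteristics. Cohort 2: "This assumes 80% power with a one-sided Type 1 error of 10%, a historical PFS(6) of 18" percent, with "one-year accrual, one-year follow-up, a target PFS(6) of 38" percent. Cohort 3 has the same error and power for "a historical median PFS(4) of 18% and a target PFS(4) of 38" percent. The Protocol synopsis says that all distributions are assumed exponential.

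The visible text of SAP 7.5.2 and 7.5.4 has no grouped null, no interval-censored analysis and no sensitivity analysis for assessment timing.

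**The concern.** A one-sample log-rank test compares observed events with expected events, which are the null hazard multiplied by total recorded PFS time. A child whose tumour progresses between scans goes on adding null hazard until the next scan. When scan gaps are large relative to the null mean, expected events exceed observed events even if the drug does nothing, and the excess counts as evidence of benefit.

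This is the primary test in six arms (A2–A4 and B2–B4), with no concurrent control to expose the error. SAP 7.5.4 also uses the significance of the same test to define success in the Cohort 2–3 futility simulation, so an inactive regimen could be harder to stop.

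**Working it through.** **The plan's own figure.** Cohorts 2 and 3 have HR = ln(0.38)/ln(0.18) = 0.564. Events needed are about (1.2816 + 0.8416)² / (ln 0.564)² = 13.77. Dividing by the event probability under the target (0.94 and 0.98) gives N = 14.7 and 14.0. The one-sample log-rank formula with variance (O+E)/2 gives 14.96 and 14.94, so 15 each, as planned. All of these formulas treat event times as exactly observed.

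**Null hazards per month** (1 month = 30.4375 days, SAP 8):
- Cohort 2, test null: ln 2/2.25 = 0.308; mean 3.25 months (14.1 weeks).
- Cohort 2, design null: −ln(0.18)/6 = 0.286; mean 3.50 months (15.2 weeks), median 2.43 months.
- Cohort 3: −ln(0.18)/4 = 0.429; mean 2.33 months (10.1 weeks).
- Cohort 4: ln 2/2.1 = 0.330; mean 3.03 months (13.2 weeks).

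**The mechanism in one interval.** In Cohort 3 the first gap is 42/30.4375 = 1.380 months. With all events scan-dated, every child who reaches or progresses at the first scan is charged 0.429 × 1.380 = 0.592 expected events. The null probability of an event in that gap is 1 − exp(−0.592) = 0.447. For an 8-week gap (1.840 months) the figures are 0.789 and 0.546.

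**Effect on mean PFS.** Scan-dating lengthens mean PFS from 3.25 to 4.12 months (Cohort 2, 2.25-month null), from 2.33 to 3.18 (Cohort 3) and from 3.03 to 3.90 (Cohort 4). Expected events rise by 27%, 37% and 29%; the rise is 25% for Cohort 2 at its 18% null. In Cohort 3, E is about 15 × 1.37 = 20.5 while O is about 15. The average Z is then (20.5 − 15)/√20.5 = 1.2, close to the critical value 1.2816 with no drug effect.

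**Simulation.** Exponential times, 12 months' accrual plus 12 months' follow-up, rejection when (E − O)/√E > 1.2816. The true hazard equals the stated null. The share of exactly dated events is not in the documents, so it is varied.

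| Share dated exactly | Cohort 2 (18% / 2.25-month null) | Cohort 3 | Cohort 4 |
|---|---|---|---|
| All | 7% / 7% | 7–8% | 7% |
| Three quarters | 11% / 11% | 13% | 10% |
| Half | about 16% (15–17% over repeat runs) | 21% | 14% |
| None | 28% / 30% | 43% | 24% |

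The SAP does not state the variance. With (O+E)/2 and no exact dates, the results are 31–34%, 47% and 28%.

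**If the historical rate was scan-read.** A landmark read from scan-dated data is the true progression-free proportion at the last scan before it. All trial events are scan-dated here.
- Cohort 2 landmark: 6 × 30.4375/7 = 26.1 weeks. On this trial's grid the last scan is week 20. Error is about 5% (18% null) or about 10% (2.25-month null).
- Cohort 2 with the last historical scan at week 24: 18% or 29%. Schedules of 4, 6, 8 and 12 weeks all end at week 24, so they are one scenario.
- Cohort 3 landmark: 4 × 30.4375/7 = 17.4 weeks. With the last scan at week 12 (this grid, or 6- or 12-weekly) error is about 5%; at week 16 (4- or 8-weekly) it is 31%.
- Cohort 4: 1% to 25% for an assumed true historical median of 6 to 9.1 weeks.

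Exactly dated events lower these further. On this trial's grid, half exact gives about 1.5% (Cohort 2, 18% null) and 0.8% (Cohort 3).

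**Grouped test.** For each scheduled interval at risk, expected events are p = 1 − exp(−null hazard × interval length), with variance p(1 − p). If every child at risk at the start is charged the full interval, error is 8–9%. Power is 79% (Cohort 2, 18% null), 86% (Cohort 2, 2.25-month null), 80% (Cohort 3) and 82% (Cohort 4). If an exactly dated child's interval instead stops at the event, then with half the events exact, error falls to 3–4% and power to 65–69% in Cohorts 2 (18% null) and 3.

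**The case against.** The strongest reply is that the historical PFS was probably scan-dated too, so like is compared with like. On a matching grid this stands, and it over-corrects: Cohort 3, and Cohort 2 at its 18% null, fall below 10%. It fails where the last historical scan fell just before the landmark (week 24 in Cohort 2, week 16 in Cohort 3). The documents do not show which applies.

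A second reply is that many events escape the grid. Deaths carry their own date, clinical deterioration can count as progression (Protocol Table 9.1.3-1), and earlier scans are allowed when medically indicated. This also stands: at three quarters exact, the error is only 10–13%.

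Third, the stated objectives are to estimate PFS in a non-randomised Phase 1b/2 trial, and the Kaplan-Meier output does not depend on the test. That lowers the severity, but SAP 5 still claims a specific error rate.

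A reader might infer that the true error in Cohorts 2 and 3 is 18–43%, or that scan-dating in the historical data can never cancel the bias. The documents support neither. Half-exact dating already puts Cohort 2 below 18%, and a matching historical grid takes both cohorts to about 5%. A reader might also conclude that the primary test must be replaced. That goes too far: if the historical rate came from this trial's grid, the grouped test would have an error of only 0.6% (Cohort 2) and 0.1% (Cohort 3).

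**Conclusion.** The concern holds as a statement about what is assured. The 10% in SAP 5 describes a test on exactly observed event times, and the plan does not produce such times. Against a continuous null the error can reach about 30% (Cohort 2), 43% (Cohort 3) and 24% (Cohort 4). Under a historical rate read on this trial's grid it is about 5–10% (Cohort 2) and 5% (Cohort 3).

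The position within that range rests on two inputs that the documents do not give: how the historical figures were assessed, and what share of events is dated off the grid. The simulations also assume exponential times and analysis after 12 to 24 months of follow-up.

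Separately, the Cohort 2 test null (2.25 months) is stricter on the drug's comparator than the 18% design rate implies (2.43 months): it sets a shorter historical PFS to beat. If 18% is true, that alone gives about 13% error with exact dates and 41% with all events scan-dated.

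This should be fixed before the primary analysis, because it changes what a positive result can support. It does not invalidate the planned test or the PFS estimates.

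**What to change.** 1. In SAP 5 and 7.5.2.2, state that the one-sided 10% holds only for exactly observed event times. Report the simulated error range under the planned scan schedule.
2. State how each historical PFS figure was assessed, including scan intervals and how progression was dated.
3. Prespecify the grouped one-sample test as a sensitivity analysis for the final test, and for the success criterion in the Cohort 2–3 futility simulation (SAP 7.5.4). Say explicitly that the full scheduled interval is charged to every child at risk at its start, including those with exactly dated events.

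The planned log-rank test, Kaplan-Meier curves and medians can stay. The cost is SAP wording, a short simulation and a few lines of code, with no new data or patients. The downside is a less favourable stated error rate, and a sensitivity test that is conservative if the historical rate was itself inflated by scan-dating.
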